2.2. Sample Size and Power Considerations

For the primary endpoint, the enrollment of 60 patients per treatment group will provide 96% power to detect a 35% difference between the most efficacious REGN3500 SC dose and the placebo group with respect to percent change in EASI score from baseline to week 16, assuming the common standard deviation (SD) is 50%, with a 2-sided test at the 0.05 significance level. The 50% SD along with the 35% difference in the mean percent were estimated based on results from two phase 3 dupilumab AD studies (R668-AD-1334 and R668-AD-1416).

The above calculation is for the full enrollment. However, the number of randomized patients is 129 in 5 arms including 6 Japanese patients because the Sponsors decided to stop the study prematurely due to the lack of efficacy in REGN3500 based on AD-1798 interim look data.

2.3. Study Plan

After providing informed consent, patients will be assessed for study eligibility at the screening visit. Patients will undergo screening within 5 weeks (ie, 35 days) prior to randomization. During the screening period, treatments for AD will be washed out, as applicable, according to eligibility requirements. Patients may be re-screened once if they fail the screening evaluation for reasons related to incidental transitory conditions (eg, medication use, concomitant illness, medical condition), unless the reason for the screen failure is related to failing the disease severity inclusion criteria.

Patients will be required to apply moisturizers (bland emollients) at least twice daily for at least the 7 consecutive days immediately before randomization (ie, baseline/randomization visit would be the eighth day) and throughout the study. However, to allow adequate assessment of skin dryness, moisturizers should not be applied on any area(s) of lesional or non-lesional skin designated for such assessments for at least 8 hours before each clinic visit.

Patients who continue to meet eligibility criteria will undergo day 1/baseline assessments and will be randomized in a 1:1:1:1:1 ratio to 1 of 5 treatment regimens (REGN3500 300 mg SC Q2W, REGN3500 300 mg SC Q4W, REGN3500 100 mg SC Q4W, REGN3500 30 mg SC Q8W, or placebo SC Q2W) during the 16-week double-blind treatment period followed by a 20-week post-treatment follow-up period.

Randomization will be stratified by baseline disease severity (moderate [IGA=3] vs. severe [IGA=4] AD). It is planned that at least approximately 50% of patients randomized will have an IGA score of 4. To ensure enrollment according to intended distribution of disease severity, alerts will be built into the interactive voice response system/interactive web response system (IVRS/IWRS) to limit enrolling patients with an IGA score <4.

Patients will remain at the study site for a minimum of 30 minutes after administration of study drug, and the monitoring period may be extended up to 2 hours as per country-specific requirements. During the 16-week treatment period, patients will have study visits every other week. The end-of-treatment (EOT) visit will occur at week 16, which is 2 weeks after the last dose of study drug. The primary endpoint will be determined at week 16.

Post-treatment follow-up visits will occur every 4 weeks from week 20 through week 36. The duration of the 20-week post-treatment follow up period is based on the time expected for REGN3500 drug levels to reach zero (below the lower limit of quantification) in most patients after the last dose of REGN3500. The end of study (EOS) visit will occur at week 36. Efficacy will be assessed using various outcome measures of severity and extent of AD (EASI, SCORAD, IGA, GISS, BSA), patient-reported symptoms (PRO) measures of symptoms (Pruritus NRS, Pain NRS, Sleep Quality NRS, outcome Patient Oriented Eczema Measure [POEM]), mood (Hospital Anxiety and Depression Scale [HADS]), and QOL (Dermatology Life Quality Index [DLQI]).

Safety and tolerability will be monitored by clinical assessment of adverse events (AEs) and by repeated measurements of clinical evaluation including vital signs (body temperature and sitting blood pressure, pulse, and respiration rate), physical examinations, eye examinations, 12-lead electrocardiograms (ECGs), and laboratory assessment including standard hematology, chemistry, and urinalysis.

Blood samples for the determination of functional REGN3500 and ADA in serum will be collected. Serum and plasma samples will also be collected for analysis of additional biomarkers, including total IL-33, thymus and activation-regulated chemokine (CCL17; TARC), total IgE, high-sensitivity C-reactive protein (hs-CRP), and serum amyloid A (SAA). Following the initial dose of study drug administered SC on day 1, study treatment will be administered SC through week 14. The last study treatment will be administered at week 14. If medically necessary (ie, to control intolerable AD symptoms), patients may receive rescue treatment for AD (eg, systemic and topical corticosteroids) at the discretion of the investigator.

The study event table is presented in Section [10.2](#).

3. ANALYSIS POPULATIONS

In accordance with guidance from the International Conference on Harmonization of Technical Requirements for Registration of Pharmaceuticals for Human Use (ICH) guideline ICH E9 Statistical Principles for Clinical Trials (ICH, 1998), the following population will be used for all statistical analysis as specified below:

3.1. The Full Analysis Set (FAS)

The full analysis set (FAS) includes all randomized patients; it is based on the treatment allocated (as randomized). Efficacy endpoints will be analyzed using the FAS.

3.2. The Safety Analysis Set (SAF)

The safety analysis set (SAF) includes all randomized patients who received any study drug; it is based on the treatment received (as treated). Treatment compliance/administration and all clinical safety variables will be analyzed using the SAF.

The actual treatment group as treated is defined by the following rules:

- For a patient randomized to receive REGN3500, if the patient received all placebo injections, the actual treatment will be assigned as placebo.
- For a patient randomized to receive REGN3500, if the patient received at least one REGN3500 injection as planned, the actual treatment will be same as the planned treatment.
- For patients randomized to receive matching placebo for REGN3500 but accidentally received REGN3500 once injection, the actual treatment will be assigned as REGN3500.

The safety analysis will be performed separately for the treatment period, follow-up period and overall study period as defined below.

Treatment period: from the date of the first dose of study drug to the date of the end of treatment which is defined as:

- the date of Week 16 visit (or study day 113 starting from the first dose of study drug if the date of the Week 16 visit is unavailable for those patients who completed the 16 week)
- the date of early termination visit, for those patients who did not complete the Week 16 visit
- 12Feb2020 for the patients who were early terminated from the treatment per Sponsor's decision to stop the study on 12Feb2020 and Week 16 visit or early termination visit is unavailable.

Follow-up period: from the date of the end of the treatment to the date of the end of study visit

Overall study period: from the date of the first dose of study drug to the date of the end of study visit

For the analyses of follow-up period, only a subset of SAF will be included, which is defined as the patients who entered the follow-up period and had at least one visit during the follow-up period.

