10.4.4.1. Adverse Events

Definitions

For safety variables, 2 observation periods are defined:

- The pretreatment period is defined as the time from signing the ICF to before the first dose of study drug.
- The treatment-emergent period is defined as the day from first dose of study drug to the end of study. The treatment-emergent period includes the 16-week treatment period and follow-up period.
 - Treatment period: date of the first dose of study drug to week 16 visit date (study day 113 starting from the first dose of study drug if week 16 visit date is unavailable) or ET date, whichever comes first.
 - Follow-up period: date after week 16 visit date (study day 113 starting from first dose of study drug if week 16 visit date is unavailable) to EOS visit.

Treatment-emergent AEs are defined as those that are not present at baseline or represent the exacerbation of a pre-existing condition during the treatment-emergent period.

Analysis

All AEs reported in this study will be coded using the currently available version of the Medical Dictionary for Regulatory Activities (MedDRA[®]). Coding will be to lowest level terms. The verbatim text, the preferred term (PT), and the primary system organ class (SOC) will be listed.

Summaries of all TEAEs by treatment group and for overall during the treatment-emergent period, during the 16-week treatment period, and during the follow-up period will include:

- The number (n) and percentage (%) of patients with at least 1 TEAE by SOC and PT
- TEAEs by severity (according to the grading scale outlined in Section 9.5.1), presented by SOC and PT
- TEAEs by relationship to treatment (related, not related), presented by SOC and PT
- Treatment-emergent AESIs (defined with a PT or a prespecified grouping)

Deaths and other SAEs will be listed and summarized by treatment group.

Treatment-emergent AEs leading to permanent treatment discontinuation will be listed and summarized by treatment group.

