6.4. Visit Windows

Data analyzed by-visit-analysis (including efficacy, laboratory data, visit sign, ECG, ADA) will be summarized by the study scheduled visits described in the study protocol and SAP "Schedule of Events". The analysis visit windows will be exhaustive so that all available values obtained from unscheduled visits and early termination (ET) visit have the potential to be summarized. No analysis visit windows will be applied for the study scheduled visits.

The following analysis visit windows will be used to map the unscheduled visits:

Visit	Target Day	Analysis Time Window Based on Study Day*
Screening	<1	<1
Baseline	1	1
Week 2	15	[2, 21]
Week 4	29	[22, 36]
Week 6	43	[37, 50]
Week 8	57	[51, 64]
Week 10	71	[65, 78]
Week 12	85	[79, 92]
Week 14	99	[93, 106]
Week 16	113	[107, 127]
		Analysis Time Window Based on Days Relative to Treatment Period End Date**
Week 20	28	[1, 42]
Week 24	56	[43, 70]
Week 28	84	[71, 98]
Week 32	112	[99, 126]
Week 36	140	≥ 127

*study day is calculated relative to the date of first study drug injection.

** Days relative to treatment period end date =visit date –the treatment period end date.

If the early termination (ET) occurs during the treatment period, it will be mapped to next scheduled visit during the period. Similarly, it occurs during the follow-up period, it will be mapped to the next scheduled visit during the follow-up period:

For patients who discontinued from the treatment due to the sponsor’s decision to stop study, the Week 16 will be mapped to the patients’ next scheduled visit.

In general, the following order will be used to select the record for analysis at given visit:

1. Scheduled visit
2. Early termination (ET) if scheduled visit not available
3. Unscheduled visit if both scheduled visit and ET are not available

For the multiple measurements of the same test in the same window, the following rules will be used to pick up the analysis value:

- If multiple valid values of a variable within an analysis visit window, the closest from the target study day will be selected.
- If the difference is a tie, the value after the targeted study day will be used.
- If multiple available values of a variable exist within a same day, then the first value of the day will be selected.

Both scheduled and unscheduled measurements will be considered for determining abnormal/PCSV values from laboratory, vital sign or ECG as well as the baseline values.

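### SAP 3.2 drops the protocol's day-113 cap on the treatment period, so for some patients without a Week 16 visit a late early termination visit carries follow-up time into it

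*SAP*

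**What the plan says.** Protocol 10.4.4.1 runs the treatment period from first dose to the Week 16 visit date, with a fallback and a cap: "study day 113 starting from the first dose of study drug if week 16 visit date is unavailable) or ET date, whichever comes first". An ET visit after that point cannot lengthen the period.

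SAP 3.2 defines the end of treatment by three bullets, with no order among them:

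- **Bullet 1:** the Week 16 visit date. Day 113 is used only "if the date of the Week 16 visit is unavailable for those patients who completed the 16 week".
- **Bullet 2:** "the date of early termination visit, for those patients who did not complete the Week 16 visit".
- **Bullet 3:** 12 February 2020 for patients taken off treatment "per Sponsor's decision to stop the study on 12Feb2020 and Week 16 visit or early termination visit is unavailable".

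SAP 6.4 foresees an ET visit after treatment has ended: if "it occurs during the follow-up period, it will be mapped to the next scheduled visit during the follow-up period". Protocol 8.1.2 ties the ET visit to withdrawal from the study. Patients who only stop study drug are asked to stay on the visit schedule. SAP 1.2.4, which lists departures from the protocol's statistical section, does not mention the new definition.

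**The concern.** Under the protocol, a patient who misses Week 16 and withdraws during follow-up leaves the treatment period at day 113. Under bullet 2 the same patient leaves it on the ET date, whenever that is. The rule is also circular. SAP 6.4 must know whether an ET visit fell in treatment or follow-up in order to map it, while SAP 3.2 uses that same visit to draw the boundary.

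The end date feeds several outputs:

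- the adverse event tables by period, and the event rates per 100 patient-years, which SAP 5.8.1 restricts to the treatment period;
- the laboratory, vital-sign and ECG summaries by period;
- the subset analysed for follow-up, which requires a visit in that period;
- the follow-up windows for unscheduled visits and the e-diary weeks, both counted from the end date.

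Follow-up events and time could therefore be reported as treatment-period experience and be missing from the follow-up tables. Where two bullets apply, two programmers could derive different dates.

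**Working it through.** **The plan's own figure.** Study day = 7 × week + 1, as in the schedule of events. Week 16 gives 7 × 16 + 1 = 113, the stated fallback. Likewise Week 8 = 57, Week 14 (last planned dose) = 99, Week 20 = 141, Week 28 = 197 and Week 36 = 253.

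**Effect of the missing cap.** Take a patient with no Week 16 visit, not a 16-week completer and not sponsor-stopped, last dosed on day 57. Protocol end = min(113, ET day). SAP bullet 2 end = ET day.

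| ET day | Protocol end | SAP end | Excess | Days after last dose: protocol / SAP |
|---|---|---|---|---|
| 141 | 113 | 141 | 28 | 56 / 84 |
| 197 | 113 | 197 | 84 | 56 / 140 |
| 253 | 113 | 253 | 140 | 56 / 196 |

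The excess is ET day − 113, whatever the day of the last dose. For an ET visit on or before day 113 it is zero and the two documents agree. Day 253 is a bound, because a patient who reaches Week 36 has an end-of-study visit instead.

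**Bullets 1 and 2 overlap.** A patient dosed through day 99 misses Week 16 and withdraws with an ET visit at Week 26 (7 × 26 + 1 = 183). Bullet 1 gives day 113 if this patient counts as having completed 16 weeks, a term the SAP does not define. Bullet 2 gives day 183. The gap is 70 days.

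**The word *or* in bullet 3.** A patient is stopped by the sponsor on day 57, has no end-of-treatment visit, and has an ET visit 84 days later, on day 141. If *or* means that either visit is missing, the end is day 57. If it means that both are missing, bullet 3 does not apply and bullet 2 gives day 141. The protocol rule gives min(113, 141) = 113.

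**Person-time.** In the extreme case one patient's treatment-period time goes from 113/365.25 = 0.31 to 253/365.25 = 0.69 patient-years, a factor of 253/113 = 2.24. For an arm, assume 129/5 ≈ 26 patients and a rate denominator equal to treatment-period time.

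- If all 26 contribute 113 days (26 × 113 = 2,938), one affected patient adds 28/2,938 = 1.0% to 140/2,938 = 4.8%.
- If the other 25 average only 57 days (25 × 57 + 113 = 1,538), the range is 28/1,538 = 1.8% to 140/1,538 = 9.1%.

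**Windows and diary weeks.** In SAP 6.4 the last treatment window for unscheduled visits closes at day 127, and follow-up windows open one day after the treatment-period end. With an end at day 141, unscheduled visits on days 128 to 141 fit no window (14 days). With an end at day 197 the hole is 70 days. Diary week = floor((day − 1)/7) + 1, so days 113 to 141 become treatment weeks 17 to 21, while follow-up numbering also starts at week 17.

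**The case against.** The strongest reply is that few patients can meet the conditions. Patients off drug stay on the visit schedule, so many will have a Week 16 visit. SAP 2.1 has sponsor-stopped patients finish end-of-treatment assessments before follow-up, and SAP 6.4 implies that this visit is recorded as Week 16, so bullet 1 covers them. All analyses are descriptive. Every event from first dose to end of study remains treatment-emergent, and only its period changes. All of this stands, and it limits the size of the point.

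Three stronger readings are tempting, but the documents do not support them.

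- **That everyone without a Week 16 visit is affected.** Bullet 1 keeps day 113 for completers, and bullet 3 covers sponsor-stopped patients.
- **That the dropped phrase triples the period.** With first dose on 1 January 2020, the stop on 12 February is day 43 and an ET visit on 6 May is day 127. Bullet 2 exceeds bullet 3 by 127 − 43 = 84 days (127/43 = 2.95). That compares two SAP bullets. Against the protocol cap the excess is 127 − 113 = 14 days, a factor of 1.12. The protocol period itself can include off-drug time, up to 112 days after a single day-1 dose.
- **That scheduled follow-up visits fall outside every window.** SAP 6.4 applies windows only to unscheduled visits, so scheduled visits keep their labels.

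The reply does not remove the uncapped bullet, the overlap or the ambiguity. No other SAP section repairs them.

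**Conclusion.** The point holds in a limited form. For a patient with no Week 16 or end-of-treatment visit who is outside bullets 1 and 3, an ET visit after day 113 lengthens the treatment period by ET day − 113: 28 days at Week 20, 84 at Week 28, and at most 140. Separately, a fully dosed patient who misses Week 16, and a sponsor-stopped patient whose only closing visit is an ET visit in follow-up, each have two possible end dates.

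The documents do not say how many patients are in these positions, and the number is probably small. The arm-level percentages rest on equal arms and on the assumed average treatment-period times. No hypothesis test is affected. The change is still worth making, because the abbreviated report includes safety tables split at this date, the departure from the protocol is undeclared, and the remedy is one derivation.

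**What to change.** Replace the three bullets with an ordered rule and use the first line that applies:

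1. Week 16 or end-of-treatment visit date, if available.
2. For sponsor-stopped patients with no end-of-treatment visit and no ET visit before follow-up entry: 12 February 2020.
3. For all other patients with an ET visit: the earlier of the ET date and study day 113.
4. For patients who completed 16 weeks with neither a Week 16 nor an ET date: day 113.

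Define follow-up entry (for example, the first attended follow-up visit) and 16-week completion. Restoring the protocol sentence alone would not be enough: it has no rule for the sponsor stop, and its fallback gives day 113 to a patient lost early with neither visit, which adds unobserved time. The SAP gives that last group no end date unless they were sponsor-stopped. The same edit should name one.

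List the departure from protocol 10.4.4.1 in SAP 1.2.4. The cost is SAP wording and one derivation before database lock, with no data collection. A count of patients with no Week 16 or end-of-treatment visit and an ET visit after day 113 or after follow-up entry would show the actual extent.

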4.2.2. Secondary Endpoints

The secondary endpoints are:

Efficacy:

- Proportion of patients achieving EASI-50, EASI-75, and EASI-90 ($\geq 50\%$, $\geq 75\%$, and $\geq 90\%$ improvement from baseline) at week 16
- Absolute change in EASI scores from baseline to week 16
- Proportion of patients with both an IGA score of 0 or 1 (on a 5-point scale) and a reduction from baseline of ≥ 2 points at week 16
- Change (absolute and percent) from baseline to week 16 in weekly average of daily peak Pruritus Numerical Rating Scale (NRS)
- Proportion of patients with improvement (reduction) of weekly average of daily peak Pruritus NRS ≥ 4 from baseline to week 16
- Time to onset of effect on pruritus during the 16-week treatment period (≥ 4 -point reduction of weekly average of daily peak Pruritus NRS from baseline)
- Percent change from baseline to week 16 in SCORing Atopic Dermatitis (SCORAD)
- Change from baseline to week 16 in percent BSA of AD involvement

Safety:

- Incidence of treatment-emergent adverse events (TEAEs) from baseline through end of treatment (week 16)
- Incidence of treatment-emergent serious adverse events (SAEs) from baseline through end of treatment (week 16)
- Incidence of treatment-emergent adverse events of special interest (AESIs) from baseline through end of treatment (week 16)
- Incidence of TEAEs from baseline through end of study (week 36)
- Incidence of treatment-emergent SAEs from baseline through end of study (week 36)
- Incidence of treatment-emergent AESIs from baseline through end of study (week 36)

Pharmacokinetic:

- Concentrations of functional REGN3500 in serum by treatment regimen at each assessment timepoint from baseline to end of study (week 36)

Any exploratory endpoints will be described in the statistical analysis plan (SAP).

Note: The safety and PK endpoints will not be included in the testing hierarchy.

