2.1. Study Design and Randomization

This is a phase 2b, randomized, double-blind, placebo-controlled, parallel-group, dose-ranging study investigating the efficacy, safety, and PK profiles of REGN3500 administered to adult patients with moderate-to-severe AD. Eligible patients must have a documented history of inadequate response or intolerance to treatment with topical AD medications. This study is intended to provide information regarding 4 different REGN3500 monotherapy dosing regimens. Each REGN3500 dosing regimen will be compared with placebo to enable robust assessment of efficacy and safety.

The study duration is up to 41 weeks, including an up to 5-week (ie, 35 days) screening period, 16-week double-blind treatment period, and 20-week post-treatment follow-up period.

Approximately 300 subjects (60 subjects per treatment group) will be recruited and randomized from approximately 60 sites. Approximately 10% of patients are planned to be enrolled in Japan; and that the Japanese patients will be randomized in 2 cohorts: a sentinel cohort of 15 patients and a second cohort of 15 patients. The randomization scheme and procedure of the Japanese patients will be the same as the rest of the patients. Independent Data Monitoring Committee will review of safety data from the first 15 Japanese patients when the 15th patient completes the Day 15 visit.

Figure 1: Study Flow Diagram

D: day; EASI: Eczema Area and Severity Index; EOS: end-of-study; EOT: end-of-treatment; Q2W: every 2 weeks; Q4W: every 4 weeks; Q8W: every 8 weeks; R: randomization; W: week

On 12 February 2020, the Sponsor decided to stop the study. At that time, 129 subjects had been randomized including 6 Japanese patients. The sponsor instructed the investigators to transition all patients in the treatment phase to the twenty-week safety-follow-up period. These patients will stop the treatment and finish the end of treatment assessments before entering into the follow-up period. All patients who were in the screening period, but had not received study investigational medicinal product (IMP), will be screen failed for the reason of sponsor decision to discontinue study.

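### SAP 3.2 puts the end-of-treatment date in both the treatment and the follow-up period, against protocol 10.4.4.1 and SAP 6.4; SAP 5.8.1 should also name the overall period for TEAE tables

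*SAP*

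**What the plan says.** SAP 3.2 sets the reporting frame for safety: "The safety analysis will be performed separately for the treatment period, follow-up period and overall study period as defined below". It runs the treatment period from first dose to the end-of-treatment date. That date is the week 16 visit (or study day 113 if a completer's visit date is unavailable), the early termination visit, or 12 February 2020 for patients stopped by the sponsor who have neither visit. The next definition is "Follow-up period: from the date of the end of the treatment to the date of the end of study visit". The third is "Overall study period: from the date of the first dose of study drug to the date of the end of study visit". Follow-up analyses use a subset of the safety analysis set: "the patients who entered the follow-up period and had at least one visit during the follow-up period".

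Protocol 10.4.4.1 draws the line differently: "Follow-up period: date after week 16 visit date". SAP 2.1 says of patients stopped by the sponsor: "These patients will stop the treatment and finish the end of treatment assessments before entering into the follow-up period". SAP 6.4 measures follow-up visits in days after the treatment-period end date, with the first window opening at day 1. It treats a diary entry as follow-up only if it is dated later than that end date.

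On table periods, protocol 10.4.4.1 asks for "Summaries of all TEAEs by treatment group and for overall during the treatment-emergent period, during the 16-week treatment period", and for the follow-up period as well. Protocol 4.2.2 lists the incidence of TEAEs, serious TEAEs and adverse events of special interest (AESIs) through week 36 as secondary endpoints. SAP 5.8.1 names the treatment and follow-up periods for TEAE tables, and SAP 5.8.2 names no period for AESIs. SAP 5.8.3 to 5.8.5 name all three periods for laboratory values, vital signs and ECG.

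**The concern.** Two adjoining reporting periods should not share a day. Here they do, and the shared day is normally the end-of-treatment visit, when adverse events are reviewed and laboratory tests, vital signs, ECG and physical examination are scheduled. According to the SAP's schedule of events, it is also the only scheduled ECG between screening and the end-of-study visit.

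A programmer who follows SAP 3.2 literally and one who follows protocol 10.4.4.1 or SAP 6.4 could obtain different follow-up counts from the same data. Findings made at the end-of-treatment visit could then be presented as post-treatment safety. Efficacy is now descriptive only, while development in other diseases continues (SAP 1.1), so the safety tables are among the outputs most likely to be reused.

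The wording of SAP 5.8.1 adds a smaller problem. Someone working from that section alone would produce TEAE tables for two sub-periods and none for the overall period. Adding the two does not give the overall incidence, because one patient can appear in both.

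**Working it through.** The plan states no figure for this point, so the check compares the definitions and counts days.

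**Where each rule puts the end-of-treatment date**

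| Source | Placement |
|---|---|
| SAP 3.2 | Last day of treatment and first day of follow-up |
| Protocol 10.4.4.1 | Treatment; follow-up opens the next day |
| SAP 6.4, visit windows | Relative day 0; the first follow-up window is [1, 42] |
| SAP 6.4, diary rule | Treatment; follow-up needs a later date |
| SAP 2.1 (sponsor-stopped patients) | End-of-treatment assessments come before entry to follow-up |
| SAP 10.2, Table 1 | V10 (EOT) stands under the treatment period; follow-up is V11 to V15 |

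SAP 3.2 stands alone. SAP 1.2.4, which lists departures from the protocol's statistical section, does not mention the boundary.

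**Day count.** Inputs from SAP Table 1: first dose on day 1, end of treatment on day 113, end of study on day 253. Both ends are taken as inclusive.

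- Treatment: 113 - 1 + 1 = 113 days.
- Follow-up as worded in SAP 3.2: 253 - 113 + 1 = 141 days.
- Sum: 113 + 141 = 254. Overall period: 253 - 1 + 1 = 253. Overlap: 254 - 253 = 1 day, which is day 113.
- Follow-up from day 114: 253 - 114 + 1 = 140 days. Sum: 113 + 140 = 253, with no overlap. The 140 equals the week 36 target in SAP 6.4 (253 - 113 = 140).

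**What the shared day reaches**

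- TEAE tables by period: a TEAE that starts on that date meets both definitions.
- PCSV counts by period: SAP 6.4 admits every scheduled and unscheduled value, so a value from the end-of-treatment visit meets both definitions if assigned by date. Assignment by visit label would avoid this, but the SAP does not say which is used.
- By-visit summaries: not affected. Scheduled visits keep their label, and the follow-up windows for unscheduled visits start at day 1.
- Listings: not affected.

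**Size per patient.** SAP 2.1 gives 129 randomized patients in five arms: 129/5 = 25.8, taken as 26. This assumes equal arms, all treated and all in the follow-up subset. Adding one patient to a follow-up count changes incidence by (k + 1)/26 - k/26 = 1/26 = 3.8 points. For 30 to 22 patients the range is 1/30 = 3.3 to 1/22 = 4.5 points. If the patient already has another follow-up event counted in the same row, the change is 0.

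**The case against.** The strongest reply is that this is loose drafting that the rest of the plan corrects. Table 1 places the end-of-treatment visit under treatment, SAP 2.1 puts its assessments before follow-up, and SAP 6.4 keeps the date out of follow-up. A programmer working by visit label would not double count a PCSV. Only events or values dated exactly on the end-of-treatment date, in patients within the follow-up subset, are at issue. The study was terminated, no hypothesis is tested, and every TEAE is listed. Most of this stands, and it limits the size of the point. It does not remove it: SAP 3.2 is the section that defines the periods, and TEAEs are placed by start date and carry no visit label to fall back on.

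Three stronger readings are tempting, and the documents do not support them.

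- A reader might infer from SAP 5.8.1 that the overall TEAE table, and with it the week 36 safety endpoints, has been dropped. SAP 3.2 requires safety analysis for the overall study period, SAP 1.2.4 does not list its removal, and where 5.8.1 does restrict a table to one period (the rates per 100 patient-years) it says so. The silence of 5.8.1 and 5.8.2 is an internal inconsistency.
- A reader might infer that the follow-up subset is undefined because the end-of-treatment visit could count as its qualifying visit. Table 1 and SAP 2.1 largely settle that it does not. A patient with a post-treatment event but no later visit is left out of the follow-up tables by the subset rule itself, not by the boundary; the overall table is where that event would be tabulated.
- A reader might take 3.8 points as an expected bias. It is only the weight of one patient in an assumed arm of 26.

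SAP 3.2 also gives no end date for a patient without an end-of-study visit. That is a missing detail and does not bear on this point.

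**Conclusion.** The boundary in SAP 3.2 conflicts with protocol 10.4.4.1 and with SAP 6.4, and nothing in the SAP shows that the change was intended. Read as written, one planned day of 253 belongs to both periods. A TEAE starting on that day, and an end-of-treatment PCSV if assigned by date, would count in both period tables for patients in the follow-up subset. Follow-up counts could therefore differ between programmers. Whether they do depends on events dated on that exact day, whose number the documents do not give and which is probably small.

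The conclusion assumes that both period limits are inclusive, which is the ordinary reading of the SAP's wording, and it uses the planned schedule. For a patient who stopped early, the shared day is the early termination visit, or 12 February 2020 where SAP 3.2 sets that date.

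The secondary point is one of alignment: SAP 5.8.1 is narrower than SAP 3.2, protocol 10.4.4.1 and the week 36 endpoints, and should match them. Both are modest points, worth correcting because the correction is simple.

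**What to change.** - **SAP 3.2:** start the follow-up period on the day after the treatment-period end date. State that data from the end-of-treatment or treatment-period early termination visit count in the treatment period only, and that this visit does not qualify as a follow-up visit. Leave the subset rule otherwise unchanged. This restores the protocol's boundary and agrees with SAP 2.1, SAP 6.4 and Table 1.
- **SAP 5.8.1 and 5.8.2:** state that TEAE, serious TEAE and AESI tables are also produced for the overall study period on the full safety analysis set, as 5.8.3 to 5.8.5 already do for their data.

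The cost is a short edit in 3.2 and one sentence in each of 5.8.1 and 5.8.2. No new data are needed. The overall-period tables are descriptive and already fall under the general rule in SAP 3.2.
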